3. STUDY ENDPOINTS

The study endpoints will be evaluated after the initial treatment period and after the extension period. The results of the initial treatment period will be the basis of the primary evaluation of efficacy.

The primary efficacy endpoint in [Section 3.1](#) will be based on the Modified International Cooperative Ataxia Rating Scale (mICARS) score. This modified ICARS excludes items 17-19 related to oculomotor function, and Items 8-12 related to kinetic functions from the full 100 point ICARS (see [Section 4](#)). The full ICARS, which is the validated scale and the preference of European Regulators, will also be presented as a sensitivity analysis.

3.1 Efficacy Endpoints

Initial 6-Month Treatment Period

Primary Efficacy Endpoint

- The change of the Modified International Cooperative Ataxia Rating Scale (mICARS) scores from baseline to Visit 9. The change in the full ICARS from baseline to Visit 9 will be presented as a sensitivity analysis.

Key Secondary Efficacy Endpoint

- CGI-C at Visit 9

Other Secondary Efficacy Endpoints

- The change of CGI-S (structured) score from baseline to Visit 9.
- The change of VABS score from baseline to follow-up based on repeated measures at Visit 6 and Visit 9

Tertiary Efficacy Endpoints

- The change of QOL scores (EQ-5D-5L scale) from baseline to follow-up based on repeated measures at Visit 6 (“Month 3”) and Visit 9 (“Month 6”)

Supplemental Analysis

The modified ICARS will be rescored, using two separate methods, collapsing categories within specific items. Each method will result in a smaller total sum score across the ICARS domains. These will be referred to as Rescored mICARS Method 1 (key opinion leader [KOL] suggested) and Rescored mICARS Method 2 (CCI definition), to prevent confusion with modified ICARS. Details of the mapping to each of these abbreviated scales are presented in [Appendix II](#) and [Appendix III](#), respectively, of this document.

Extension Treatment Period (Months 6 to Month 12 of the study)

For the Extension Treatment Period, comparisons will be made for the ‘Modified’ ICARS, CGI-C, CGI-S (structured), VABS, and QoL [EQ-5D-5L] using the same methods as for the initial treatment period with missing values imputed in the same way. In addition, the full ICARS, Rescored mICARS Method 1, and Rescored mICARS Method 2 will be evaluated using the same methods as the modified ICARS.

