16 STATISTICAL METHODS

16.1 Analysis of Efficacy

Primary Efficacy Endpoint

The primary efficacy endpoint will be the change from baseline to the follow-up assessments at Days 90 and 180, in the total score on the ‘Modified’ International Cooperative Ataxia Rating Scale (ICARS).

Key Secondary Efficacy Endpoint

The key secondary efficacy end point is the CGI-C rating of change from baseline at the follow-up assessments at Days 90 and 180.

Other Secondary Efficacy Endpoints

The following secondary efficacy endpoints will be assessed in the study:

- The change of CGI-S score from baseline to follow-up based on repeated measures at Days 90 and 180
- The change of VABS score from baseline to follow-up based on repeated measures at Days 90 and 180

Tertiary Efficacy Endpoints

The following tertiary efficacy endpoint will be assessed in the study:

- The change of QOL scores (EQ-5D-5L scale) from baseline to follow-up based on repeated measures at Days 90 and 180.

This measure will be considered exploratory.

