5.1.3 Handling Missing Data

Baseline Values

If values are missing at the baseline visit (Day 0/1), and the data are also recorded at screening, then the screening value will be used in the summaries and calculations of change from baseline. Otherwise, the baseline value will be missing for safety and efficacy endpoints.

Missing Efficacy Assessments

The missing data methods are an integral part of the data analysis for efficacy and are described in full in [Section 5.3](#). For the primary analyses of mICARS, the use of a mixed-effect model repeated measure (MMRM) model allows for missing data and assumes the data are missing completely at random (MCAR), so no imputations will be performed.

For sensitivity analysis, several multiple imputation methods will be used:

1. Impute all missing data within the original treatment group.
2. Impute all data missing due to COVID-19 related restrictions to the original treatment group and impute from the control group (Jump to Reference) for all other missing data. The COVID-19 disruption is across the entire study and can be considered as random across subject characteristics and factors that may be related to treatment or outcome, so imputation assuming Missing at Random should be appropriate. Additional factors, such as the number of treatments received, can be added to the imputation model. Details to show that these subjects continued their visits up to the point of restrictions being imposed by the pandemic and did not discontinue treatment due factors related to the study protocol or outcome will be provided.
3. Impute all missing data from the control group (Jump to Reference).

In addition, last observation carried forward [LOCF] and observed cases [OC] will be used. The LOCF method will employ the last observation carried forward; this may be the baseline value if the subject has no follow-up values. The OC method will employ only observed cases for the time points of interest (i.e., for repeated measures analysis of Visit 6 [“Month 3”] and Visit 9 [“Month 6”] both mICARS must be observed/collected to be included in the analysis). A specific analysis using retrieved dropouts will not be performed (see [Section 5.10](#)).

Missing data for all other efficacy analyses not using MMRM will use Multiple Imputation #1 as described above), with the other imputation methods, LOCF and OC, for sensitivity.

Missing Values When Computing Instrument Scores

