5.3.3 Other Secondary Efficacy Variables

CGI-S (structured)

The analysis of the change from baseline to Visit 9 (“Month 6”) of CGI-S (structured) score will be performed similar to the analysis of the CGI-C score, modifying the approach using baseline as a covariate. The analysis for the extension treatment period will be performed in a similar way. For the extension treatment period, the change from baseline will be the change from the last assessment prior to first infusion in the study except for the placebo subjects who switch to EDS-EP at Visits 9 and 12 (“Month 6” and “Month 9”, respectively). For these subjects who are switched, the baseline will be the assessment just prior to the switch.

Ordinal logistic regression analyses will also be performed for CGI-S (structured) in a manner similar to CGI-C, with the exception that baseline CGI-S (structured) score will enter into the analysis.

The CGI-S score at baseline and all visits during the initial treatment period and extension treatment period (Visit 6, Visit 9, Visit 12, and Visit 15) will be summarized using summary statistics appropriate for continuous or categorical data by treatment group. The change from baseline to all visits will also be summarized and compared between treatment groups. Percent change from baseline will be summarized descriptively.

For the FAS only, the mean CGI-S score will be plotted over time during the initial treatment period with separate trend lines for each of the three treatment groups. This type of plot will be repeated for mean CGI-S score and mean change from baseline in CGI-S score over the entire study, with separate trend lines for the seven possible dosing schemes.

VABS

The analysis of the change from baseline (Day 0) to Visit 9 (“Month 6”) of VABS score will be performed using ANCOVA with LOCF score from baseline to Visit 9 (“Month 6”). Sensitivity analyses will be based on OC. The analysis for the extension treatment period will be performed in the same way. For the extension treatment period, the change from baseline will be the change from the last assessment prior to first infusion in the study except for the placebo subjects who switch to EDS-EP at Visits 9 and 12 (“Month 6” and “Month 9”, respectively). For these subjects who are switched, the baseline will be the assessment just prior to the switch.

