The VABS score at baseline and all visits during the initial treatment period and extension treatment period (Visit 6, Visit 9, Visit 12, and Visit 15) will be summarized using summary statistics

appropriate for continuous data by treatment group. The change from baseline to all visits will also be summarized and compared between treatment groups.

For the FAS only, the mean VABS score will be plotted over time during the initial treatment period with separate trend lines for each of the three treatment groups. This type of plot will be repeated for mean VABS score and mean change from baseline in VABS score over the entire study, with separate trend lines for the seven possible dosing schemes.

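### VABS and EQ-5D-5L are defined as repeated-measures endpoints at Visits 6 and 9 but analysed by Visit 9 ANCOVA with LOCF, and SAP 5.1.3 gives a third rule

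*SAP*

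**What the plan says.** **Endpoint.** SAP 3.1 gives VABS as "The change of VABS score from baseline to follow-up based on repeated measures at Visit 6 and Visit 9", and EQ-5D-5L has parallel wording. Protocol 16.1 agrees: "The change of VABS score from baseline to follow-up based on repeated measures at Days 90 and 180".

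**Analysis.** SAP 5.3.3 says the change in "VABS score will be performed using ANCOVA with LOCF score from baseline to Visit 9". It names no covariates and adds "Sensitivity analyses will be based on OC". It also states: "The change from baseline to all visits will also be summarized and compared between treatment groups". SAP 5.3.4 handles EQ-5D-5L in the same way as VABS.

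**Missing data.** SAP 5.1.3 says: "Missing data for all other efficacy analyses not using MMRM will use Multiple Imputation #1", with LOCF and OC as sensitivity methods. Its LOCF rule can reach back to baseline: "this may be the baseline value if the subject has no follow-up values".

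**Outputs.** The SAP table list has only LOCF and OC tables for VABS (14.2.61 to 14.2.64) and for EQ-5D-5L (14.2.65 to 14.2.68).

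**Protocol.** Section 16.2.8 names ANCOVA with LOCF, OC and OC + RDO for the secondary endpoints. The synopsis lets VABS, CGI-S and EQ-5D-5L be analysed by either the primary (MMRM) or the key secondary (ANCOVA) approach.

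**Record of changes.** SAP 5.10 explains why OC + RDO was dropped and comments on visit timing. It does not mention VABS or EQ-5D-5L.

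**The concern.** The SAP gives three instructions for one endpoint: a repeated-measures definition, a single-visit ANCOVA with LOCF, and a general rule that makes multiple imputation the main method. Two competent programmers could follow different sections and produce different main VABS results.

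The wording looks like an incomplete edit. Protocol 16.1 describes CGI-S by repeated measures as well. SAP 3.1 changes CGI-S to change at Visit 9 but leaves VABS and EQ-5D-5L as they were. CGI-S also has Imputation Method 1 tables (14.2.52 and 14.2.57), which VABS and EQ-5D-5L lack.

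The choice of LOCF matters in its own right. It assumes that a patient with no Visit 9 score has not changed since Visit 6. The MMRM specified for mICARS needs no such assumption; it relies on data being missing at random.

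**Working it through.** **1. The instructions side by side**

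| Place | Model or definition | Main handling of missing data |
|---|---|---|
| SAP 3.1; Protocol 16.1 | Repeated measures, Visits 6 and 9 | Not stated |
| SAP 5.3.3, 5.3.4 | ANCOVA, change to Visit 9 | LOCF; OC as sensitivity |
| SAP 5.1.3 | Any efficacy analysis without MMRM | Multiple Imputation #1; LOCF and OC among the sensitivity methods |
| SAP table list | 14.2.61 to 14.2.68 | LOCF and OC only |
| Protocol 16.2.8 | ANCOVA | LOCF, OC, OC + RDO |
| Protocol synopsis | MMRM or ANCOVA | Follows the approach chosen |

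No reading satisfies SAP 3.1, 5.1.3 and 5.3.3 together.

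**2. The plan's own figure, and how many patients are exposed**

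The sample size allows for 10% loss: 54 / (1 − 0.10) = 60 per group, as stated. That leaves 60 × 0.10 = 6 per arm. With the 175 patients actually enrolled, 175 / 3 ≈ 58.3 and 10% is 5.8.

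This is an upper planning figure. Protocol 9.4 asks patients who stop early to return for all Month 6 evaluations, and Protocol 11.4.11 includes VABS and EQ-5D-5L among them. The FAS requires a post-baseline assessment of the primary variable, so patients lost before any such assessment leave the analysis rather than being carried forward. Carrying a baseline score should therefore be uncommon.

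**3. Illustration of the LOCF effect**

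The documents give no VABS standard deviation, expected effect, correlation between visits or missing share. The power table is for mICARS and is not used here. All inputs below are assumptions: 58 per arm, a true effect of 0.5 SD accruing linearly (half present at Visit 6), a correlation of 0.6 between visits, an untreated decline of 0.6 SD over six months, Visit 9 missing with a probability that depends only on arm, Visit 6 always observed, and 3,000 simulated trials.

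*Equal missingness.* With missing share m and r = Visit 6 effect / Visit 9 effect, the LOCF estimate is the effect × [1 − m(1 − r)].

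| Missing in both arms | Formula | LOCF, simulated | MMRM, simulated |
|---|---|---|---|
| 0% | 0.500 | 0.499 | 0.499 |
| 10% | 0.5 × (1 − 0.10 × 0.5) = 0.475 | 0.474 | 0.499 |
| 20% | 0.5 × (1 − 0.20 × 0.5) = 0.450 | 0.449 | 0.498 |

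The loss is therefore 5% at m = 10% and 10% at m = 20%. It would be 10% and 20% if baseline were carried (r = 0), and nil if the whole effect were present by Visit 6 (r = 1). The simulated estimates vary from trial to trial with an SD of about 0.19, so a shift of 0.025 is small.

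*Unequal missingness, no true effect.* The LOCF bias is the difference in missing share × the decline between Visits 6 and 9 (0.3 SD).

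- 10% against 20% missing: 0.10 × 0.3 = 0.03; simulated 0.028.
- 5% against 20% missing: 0.15 × 0.3 = 0.045; simulated 0.043.

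The simulated MMRM estimate is 0.002 in both cases. Under an assumed decline, LOCF favours the arm with more missing data.

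**4. Complete data**

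The 0% row shows that the two models give the same Visit 9 estimate. The simulation adjusted for baseline separately at each visit; with the single baseline term in SAP 5.3.1, expect close rather than exact agreement.

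**The case against.** The strongest reply is that the protocol authorises this analysis. Section 16.2.8 names ANCOVA with LOCF for VABS, and the synopsis permits it. SAP 5.1.3 itself defers to 5.3 for the full description of efficacy missing-data methods, and the table list agrees with 5.3.3, so what would be run is fairly clear. Rewording SAP 3.1 to change at Visit 9, as was done for CGI-S, would also remove the mismatch. Observed-case and per-protocol analyses are planned alongside.

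Much of this stands. It disposes of two stronger readings:

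- *The SAP breaches the protocol or throws Visit 6 away.* It does neither. Protocol 16.2.8 supports the ANCOVA. Visit 6 change is still summarised and compared, and LOCF uses the Visit 6 score when Visit 9 is missing. Only the repeated-measures model is absent.
- *COVID gaps make dropout differ by arm, so VABS is biased.* Differential dropout is possible, but nothing in the documents shows it. SAP 5.1.3 treats the pandemic disruption as random, and the trial is double-blind.

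The objection does not remove the conflict. SAP 3.1 and the general rule in 5.1.3 still contradict 5.3.3. Rewording 3.1 alone would leave LOCF against multiple imputation unresolved and keep LOCF as the main method. MMRM fits the endpoint as both documents define it and is already allowed by the synopsis, so asking for it is more than preference.

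**Conclusion.** The contradiction is real and unresolved for VABS and EQ-5D-5L, and the protocol is itself inconsistent. The practical effect is limited. With complete data the Visit 9 estimate is the same under either model. With Visit 9 missing, LOCF can bias it, and up to about 6 patients per arm could be affected at the planned 10% loss, probably fewer.

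The size and direction of any bias cannot be computed from the documents. The figures above rest on assumed inputs. In particular, a reader might infer from the progressive course of the disease that LOCF must flatter whichever arm loses more patients. That needs a declining VABS score under placebo, and the documents give no such trajectory; the only VABS change they report is improvement in the open-label pilot.

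Nor does the point threaten the trial's success criterion. SAP 5.1.10 formally tests only mICARS and CGI-C, and EQ-5D-5L is exploratory. Protocol 16.2.8 still places VABS third among the secondary endpoints for each dose, which also needs reconciling with the SAP. This is a low-severity correction worth making before unblinding.

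**What to change.** - Make the main analysis of VABS and EQ-5D-5L the MMRM used for mICARS: the scale's own baseline, treatment, age, sex, region, visit and treatment-by-visit, reporting the Visit 9 contrast.
- Keep LOCF and OC as sensitivity analyses only.
- Align SAP 3.1, 5.1.3, 5.3.3 and 5.3.4, so that each scale has one definition, one model with stated covariates, and one main method for missing data.
- Revise Tables 14.2.61 to 14.2.68 to match.
- Record the departure from Protocol 16.2.8 in SAP 5.10, noting that the synopsis allows the MMRM approach.

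The cost is SAP wording, the revised tables and one documented change from the protocol. The primary-analysis program can be re-used, and no new data are needed.

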3.2 Safety Endpoints

Safety will be evaluated by analysis of the following parameters:

- Adverse events and related AEs;
- Serious AEs and related SAEs;
- Discontinuation due to AE;
- Laboratory results (clinical chemistry, hematology, and urinalysis);
- Special laboratory parameters (HbA1c, CD4+ lymphocytes count, α -fetoprotein, CRP, and RBC antibodies [IgG, IgM and Qualitative Direct Coombs test]);

- Sterility testing of EDS-EP;
- Vital signs;
- Physical and neurological examination findings;
- 12-lead standard ECG;
- Bone mineral density;
- Tanner staging;
- C-SSRS.

3.3 Pharmacokinetic Endpoints

Pharmacokinetic analysis will be done on the following endpoints, and full details will be provided in a separate PK Analysis Plan.

- Population PK analysis for dexamethasone administered via EDS, based on pooled data for dexamethasone plasma concentrations from all samples obtained from subjects in each of the EDS treatment groups.
- PK parameters calculated for each subject, based on plasma levels of dexamethasone: C_{max} , t_{max} , AUC, and apparent half-life.

3.4 Pharmacodynamic Endpoints

Exploratory analyses will be performed to assess the relationship of mini-ATM levels to efficacy and safety outcomes.

4. DEFINITIONS AND DERIVED VARIABLES

Study Day

Study Day 1 will be defined as the date of the start of the first infusion of study drug. Per CDISC guidelines, Study Day -1 will be day immediately preceding Study Day 1, and negative study days will be measured backwards from Study Day -1 (that is, Study Days -2, -3, -4, etc). There will be no Study Day 0 per CDISC guidelines, thus Study Day -1 will correspond to “Study Day 0” as mentioned in the protocol.

Age

Age will be calculated using the date of birth (DOB) and the date of randomization and will be presented in data displays as an integer using the integer (“int”) function in SAS. In the database, age will be given with two decimals.

$$\text{Age} = (\text{DOB} - \text{Date of Randomization}) / 365.25$$

Body Mass Index (BMI)

BMI will be calculated using weight in kg and height in m.

$$\text{BMI} = \text{Weight (Kg)} / \text{Height (m)}^2$$

The International Cooperative Ataxia Rating Scale (ICARS)

The International Cooperative Ataxia Rating Scale (Trouillas, 1997), the most frequently used clinician (neurologist) rated measure in patients with ataxias, was developed by a Committee of the

World Federation of Neurology to help standardize common manifestations of syndromes that lead to cerebellar dysfunction. The ICARS is a 100-point, semi-quantitative scale offering a compartmentalized quantification of the following 4 sub-scores: Posture and Gait Disturbances (34 points), Kinetic Functions (52 points), Speech Disorders (8 points), and Oculomotor Disorders (6 points).

To maximize the consistency of the data obtained from the ICARS, the same neurologist, well trained in the use of the ICARS and with expertise in the field of AT disorders, will evaluate the same subject at approximately the same time throughout the study. At each site, qualified raters will be trained to criteria at the Investigator's meeting and will receive ongoing training during the trial. The ICARS rater will perform the rating on each subject without consulting the results from the previous visit. In addition, video recording will be performed during each ICARS administration (though not required at Screening), according to a standardized procedure. The video recordings from each subject will be sent to an independent remote rater, where they will be blindly evaluated in random order. The speech domain items (Items 15 and 16) will be rated only by local raters who are familiar with the local language. The ICARS ratings from the independent remote rater, making use of the speech domain items which come only from the local raters, will be used for the primary efficacy endpoint analysis which is the mICARS.

Rating of the ICARS will be performed 24 hr before Baseline (Day -1) and at Baseline (Day 0); the Day 0 assessment will be recorded and used for determining changes from baseline on treatment. The ICARS will also be assessed at Visit 6 ("Month 3") and at Endpoint (Visit 9 ["Month 6"] or at early discontinuation) during the Initial Treatment Period, and at Visit 12 ("Month 9") and Visit 15 ("Month 12") (or at early discontinuation) during the Extension Treatment Period.

The ICARS score is the total sum of the sub scores and ranges from 0 to 100, with 100 being indicative of the most severely affected outcome. The 'Modified' ICARS (mICARS) score is the total sum of the sub scores excluding Items 17-19 related to oculomotor function and Items 8-12 related to kinetic function; these sub scores have been removed per **CC** request. The 'Modified' ICARS score ranges from 0 to 54, with higher scores indicative of more severely affected outcome.

The baseline score by the central rater for the ICARS will be assessed at Visit 1, and the score closest to dosing will be accepted; therefore, the Day 1 value will be used where present, otherwise the Day 0 value will be used. If both the Day 1 and Day 0 assessments are missing, the Screening value by the local rater will be used.

Initial 6-Month Treatment Period

Change from baseline will be calculated by using the following formula =

(mICARS Score at Visit 6 ("Month 3") - Baseline mICARS Score)

(mICARS Score at Visit 9 ("Month 6") - Baseline mICARS Score)

Extension Treatment Period

For subjects randomized to EDS-EP and placebo subjects who are not switched to EDS-EP (original treatment assignment), the change from baseline will be calculated by using the the last assessment prior to first dose as baseline. For the placebo subjects who are switched to EDS-EP at either Visit 9 ("Month 6") or Visit 12 ("Month 9"), the last mICARS Score prior to the switch will be used as baseline. Change will be calculated as follows:

(mICARS Score at Visit 12 ("Month 9") - Baseline mICARS Score)

(mICARS Score at Visit 15 ("Month 12") - Baseline mICARS Score)

The Clinical Global Impression (CGI-C and CGI-S [structured])

The Clinical Global Impression (CGI) consists of two 7-point, clinician-rated, Likert-type scales assessing change from baseline (CGI-C) and severity of neurological symptoms (CGI-S [structured]) (Guy, 1976).

In the current study, an overall assessment of the change in the subject's neurological symptoms of AT, compared to the status at baseline, will be made using the CGI-C. CGI-C scores range from 1 (very much improved) through 7 (very much worse). CGI-C is assessed at Visit 6 ("Month 3") and Visit 9 ("Month 6") during the initial treatment period, and at Visit 12 ("Month 9") and Visit 15 ("Month 12") of the extension treatment period.

In addition, the severity of neurological symptoms at baseline and at each subsequent time point will be assessed using the CGI-S (structured). No version of the CGI-S exists which has been specifically adapted for use in AT patients; therefore, a structured 5-point version was developed which takes into account the severity of the following symptoms of AT: ataxia (walking), dysarthria, dysmetria, extrapyramidal symptoms (chorea, myoclonus, dystonia, and tremor), and eye movements (Nissenkorn, 2015). Ratings of none, mild, moderate, severe, and very severe are selected based on the level of symptomatology. CGI-S (structured) is assessed at Visit 6 ("Month 3") and Visit 9 ("Month 6") during the initial treatment period, and at Visit 12 ("Month 9") and Visit 15 ("Month 12") of the extension treatment period.

Vineland Adaptive Behaviors Scale (VABS)

Functional intelligence generally is defined as one's ability to behave adaptively in daily life. Specifically, it includes the person's ability to express and comprehend language, behave appropriately in interpersonal situations, understand and use social behaviors, protect himself/herself, and care for himself/herself, in terms of personal hygiene and domestic independence. Although several scales and observation systems for measuring adaptive behavior have been developed since the 1940s when the construct of adaptive behavior was formally introduced, one of the most widely accepted scales is the Vineland Adaptive Behavior Rating Scales (VABS) (Sparrow, 2005).

The VABS is used primarily with children and adolescents from birth to age 18 years but may be used for adults suspected of having a mental handicap based on obtained IQ. The scale measures adaptive behavior in four major domains, Communication, Daily Living Skills, Socialization, and Motor Skills. These domains include several subdomains, as follows:

- **Communication:** Receptive, Expressive, Written
- **Daily Living Skills:** Domestic, Personal, Community
- **Socialization:** Interpersonal Relationships, Play & Leisure, Coping Skills
- **Motor Skills:** Gross, Fine.

VABS is assessed at Visit 1 (Day 0), Visit 6 ("Month 3"), and Visit 9 ("Month 6") during the initial treatment period, and at Visit 12 ("Month 9") and Visit 15 ("Month 12") of the extension treatment period. The Visit 1 result will be used as the baseline score. For the placebo subjects that switched to EDS-EP at or after Visit 9 ("Month 6"), the last assessment prior to treatment with EDS-EP will be used as baseline for the comparisons to Visit 12 ("Month 9") and Visit 15 ("Month 12").

EQ-5D-5L Quality of Life (QOL) scale

The EQ-5D-5L is assessed at Screening, Visit 1 (Day 0), Visit 6 (“Month 3”), and Visit 9 (“Month 6”) during the initial treatment period, and at Visit 12 (“Month 9”) and Visit 15 (“Month 12”) of the extension treatment period. The Visit 1 result will be considered the baseline score. For the placebo subjects that switched to EDS-EP at or after Visit 9 (“Month 6”), the last assessment prior to treatment with EDS-EP will be used as baseline for the comparisons to Visit 12 (“Month 9”) and Visit 15 (“Month 12”).

C-SSRS

The C-SSRS is assessed at Visit 1 (Day 0), Visit 4 (“Month 1”), Visit 5 (“Month 2”), Visit 6 (“Month 3”), Visit 7 (“Month 4”), Visit 8 (“Month 5”), and Visit 9 (“Month 6”) during the initial treatment period, and at Visit 10 (“Month 7”), Visit 11 (“Month 8”), Visit 12 (“Month 9”), Visit 13 (“Month 10”), Visit 14 (“Month 11”), and Visit 15 (“Month 12”) of the extension treatment period. The result at Visit 1 is the baseline score for the calculation of the change from baseline. For the placebo subjects that switched to EDS-EP at or after Visit 9 (“Month 6”), the last assessment prior to treatment with EDS-EP will be used as baseline for the comparisons to Visit 12 (“Month 9”) and Visit 15 (“Month 12”).

Prior/Concomitant Medications

Concomitant medications are any medication with use meeting at least one of the following four criteria. All other medication uses will be classified as “prior”.

- Non-study medications with a start or stop date on or after the date of the first infusion of study treatment;
- Non-study medications that started prior to the first infusion of study treatment and are ongoing during the treatment period;
- Non-study medications with partial start dates that indicate that the medication could be concomitant in relation to the date of the first infusion of study treatment;
- Non-study medications with completely missing start dates, unless their stop dates confirm otherwise (i.e. the stop date is before the first infusion of study treatment).

